10.5.2 Peripheral Blood Preparation, Storage, and Preservation

The proposed study aims to evaluate genomic alterations and or others (from a routine blood draw) for research purposes to be performed for this cohort of subjects with ER+/HER2- breast cancer. The blood samples will be prospectively collected at various time points and retrospectively evaluated (i.e., pretreatment, , Cycle 3 Day 1 and post-treatment on the study) (if post-treatment blood draw is not collected for any given reason, the treating provider may choose to do a blood sample collection at the follow-up visit).

The blood sample collection will be per Natera (Signatera™) guidelines for possible blood marker analysis for research purposes. Peripheral blood received fresh in the MCW Tissue Bank from consented participants. Sample collection kits (provided by Natera) will be used for blood collection.

Blood samples for Germline testing: Two 10 mL Streck tubes of blood will be collected pre-treatment, at Cycle 3 Day 1 and at the end of treatment for germline testing. The tube should be inverted a couple times after collection and shipped to MCW (see operations manual for further instructions).

Matched Normal Blood – in the form of frozen buffy-coat or frozen whole blood in a purple top EDTA (>1ml frozen whole blood, >200ul buffy coat). A 6 mL EDTA tube will be collected pre-treatment. The tube should be inverted a couple times after collection and shipped to MCW (see operations manual for further instructions).

10.5.3 Functional Imaging

18F-FFNP PET/CT Imaging Protocol

For this study, PR functional imaging using ¹⁸F-FFNP PET/CT will be performed for up to 12 subjects. Quantitative molecular imaging with ¹⁸F-FFNP PET/CT before and seven to 14 days after starting therapy may be useful to confirm optimal dosing of onapristone to block PR binding to ¹⁸F-FFNP in patients with extrahepatic metastases. Incomplete receptor blockade, indicating suboptimal dosing, may be associated with earlier disease progression. The change in tumor ¹⁸F-FFNP uptake after starting therapy will be evaluated as an estimate of PR binding availability. Tumor ¹⁸F-FFNP uptake parameters (SUV_{max}, SUV_{mean}, SUV_{peak}, tumor-to-normal tissue uptake ratio, functional tumor volume, and total lesion uptake) will be measured before and after starting therapy.

PET/CT scanners at UW-Madison are qualified by the American College of Radiology (ACR) Imaging Core Laboratory and have been approved for use in current ECOG/ACRIN trials. The scanner routinely will be assessed for quantitative integrity and stability by being tested using various imaging protocols on a standard phantom. For SUV measurement, this includes a comparison against a dose calibrator to ensure accuracy. A daily QC check will be performed at the beginning of the day, including PET/CT scanner and dose calibrator, in accordance with the manufacturer recommendations. If any of the QC results are outside of the manufacturer's guidelines, the study will be rescheduled, and the problem rectified before scanning any subjects. ¹⁸F-FFNP PET/CTs not completed within the protocol-specified windows due to QC results will not be considered a protocol deviation.

A PET Imaging Protocol Manual specific to this clinical trial will be prepared for the research study coordinators and nuclear medicine technologists at UW-Madison. Subjects do not need to be fasting for ¹⁸F-FFNP PET/CT imaging, but will be encouraged to be well hydrated. The subject's weight will be measured the day of imaging. ¹⁸F-FFNP will be synthesized according to cGMP requirements and processed for QA/QC by the UW Radiopharmaceutical Production Facility. For each research imaging session, subjects will receive ¹⁸F-FFNP, approximately 7 mCi (259 MBq), IV slow infusion over approximately two minutes followed by saline flush, once administered in the PET imaging suite.

After approximately 60 minutes of uptake time, the subject will be positioned supine in the PET/CT scanner (Discovery 710 or Discovery MI at UW-Madison) for a standard body PET/CT scan from skull vertex to mid-thigh (typically five to seven fields of view depending on scanner specifications and the subject's height) covering all known sites of metastatic disease and will include normal organs with expected ¹⁸F-FFNP uptake (pituitary gland and uterus). This scan will usually take approximately 20 to 30 minutes, depending upon the scanner used. Subjects will be asked to void prior to and soon after the exam to further minimize radiation dose to the urinary bladder. All sequential PET/CT imaging sessions will be performed on the same scanner to minimize variability. An iterative ordered-subsets expectation maximization algorithm will be used for PET image reconstruction. The PET data will be corrected for attenuation and scatter and co-registered with the CT images.

All adverse events occurring within a 24-hour period post-18F-FFNP infusion will be recorded from the subject within one to three days post-18F-FFNP infusion. Events to be specifically monitored during the infusion include localized discomfort at the IV injection site, pain, respiratory difficulties, flushing, dizziness, pruritus/rash, and any other symptoms that could be secondary to an anaphylactic reaction. The subject will be instructed to report any symptoms or sensory changes noted.

10.5.4 18F-FFNP PET/CT Imaging Analysis

18F-FFNP PET/CT images will be reviewed for general quality, including quality of the PET images, quality of CT images, the adequacy of PET/CT alignment, and the presence of any significant attenuation artifact. Lesions of interest will be visually identified by 18F-FFNP uptake and confirmed on at least one other conventional imaging modality, which may include the CT portion of the same PET/CT examination. Each site of disease will be analyzed for (1) qualitative and (2) quantitative 18F-FFNP uptake. For subjects with innumerable lesions, an arbitrary maximum of five lesions will be recorded.

10.5.5 Qualitative Analysis of 18F-FFNP Uptake (Lesion-Level)

18F-FFNP uptake will be evaluated qualitatively with the following scale: no uptake (tumor < background), minimal uptake (tumor = background), mild (tumor slightly > background), moderate uptake (tumor >> background), and intense uptake (tumor >>> background). Tumor uptake will be defined as increased (moderate or intense uptake) or absent (no uptake, minimal or mild uptake) for up to five target lesions.

10.5.6 Quantitative Analysis of 18F-FFNP Uptake (Lesion-Level)

Up to five target lesions with increased 18F-FFNP uptake, as defined by the qualitative analysis, will be further evaluated. Regions of interest (ROI) will be manually drawn to include the tumor and 18F-FFNP uptake will be quantified using standardized uptake value (SUV) measurements including SUVmax, SUVmean, SUVpeak, tumor-to-normal (T/N) tissue ratio, and tumor-to-blood pool ratios.

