_____ 10. An FFPE tumor biopsy block or up to 20 superplus frost slides with unstained histological sections at 4 micrometer thickness are required at the time of study entry. Archived tumor tissue acceptable (metastatic disease from non-bone and non-brain sites preferred, but primary breast or lymph node tissue is permitted) if obtained in the 18 months prior to study registration, otherwise a fresh biopsy will be required if deemed safe by the treating physician (minimal risk to patient) (see section 10.5.1). Confirmation of adequate and available tissue sample is to be determined by the site's pathologist. Tumor samples do not need to be shipped for eligibility purposes. Tumor samples do not need to be shipped until subject is confirmed eligible and is registered for treatment.

_____ 11. Ability to take oral medications (without crushing). Please refer to section 6.1.2 for directions on taking the study drug (onaprisone).

_____ 12. To participate in the optional ^{18}F -FFNP PET/CT imaging, the subject must have ER positive, HER2 negative, AND PgR positive disease and at least one extra hepatic lesion measuring at least 10 mm in size.

Exclusion Criteria

Patients meeting any of the following exclusion criteria are not to be enrolled in the study:

- _____ 1. Prior treatment with an anti-progesterone agent.
- _____ 2. Prior treatment with fulvestrant in the metastatic setting.
- _____ 3. Prior treatment with CDK4/6 inhibitors in the neoadjuvant/adjuvant setting.
- _____ 4. History of malignancy other than breast cancer within three years prior to registration except for adequately treated non-melanoma skin cancer, cervical carcinoma *in situ*.
- _____ 5. History or presence of clinically active, and symptomatic CNS metastasis: If the patient fulfills the following criteria, they will be eligible for the trial:
 - Completed prior therapy (including radiation and/or surgery) for CNS metastases \geq 28 days prior to the start of study treatment and CNS tumor is clinically stable at the time of screening and patient is not receiving steroids and/or enzyme inducing anti-epileptic medications for brain metastases.
- _____ 6. Subjects with any of the following conditions:
 - Clinically significant illness or systemic disease as determined by the treating physicians.

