8.2.6 Handling and Drug Accountability

As per institutional guidelines.

8.3 ^{18}F -FFNP

8.3.1 ^{18}F -FFNP Description

The chemical name of ^{18}F -FFNP is 21-[^{18}F] fluoro-16 α ,17 α -[(R)-1'- α -furylmethylidene) dioxy]-19-norpregn-4-ene-3,20-dione. ^{18}F -FFNP is a radiolabeled progestin analog that binds to progesterone receptor with high affinity and selectivity (7-9). In primary and metastatic breast cancer, uptake of ^{18}F -FFNP measured by PET/CT imaging has been shown to correlate with PR expression in biopsy material assayed by immunohistochemistry. ^{18}F -FFNP is primarily cleared from the body via hepatobiliary elimination.(50-54)

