10.5.7 Definition of 18F-FFNP Blockade

The same five target lesions will be analyzed for quantitative 18F-FFNP uptake on the second 18F-FFNP PET/CT examination as on the initial scan. If the SUVmax for all five lesions have decreased by > 75% or all five lesions have SUVmax < 1.5 on the second scan, then these subjects will be prospectively defined as having complete 18F-FFNP blockade. If the SUVmax for any of the five lesions has not decreased by > 75% or if any new lesions arise with SUVmax ≥ 1.5 , then these subjects will be defined as having incomplete 18F-FFNP blockade. Changes in radiotracer uptake in normal organs with expected 18F-FFNP uptake (pituitary gland and uterus) will also be measured as an internal reference.

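### The 18F-FFNP sub-study admits subjects on an extrahepatic lesion of at least 10 mm, but the blockade classification has no site or size limit, so a liver lesion can class a blocked subject as incomplete

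*Combined protocol and SAP*

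**What the plan says.** Section numbers are those in the body of the protocol, which differ from the table of contents for the PET sections.

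- **Entry.** Inclusion 12 (section 4.2) asks for ER-positive, HER2-negative, PgR-positive disease and "at least one extra hepatic lesion measuring at least 10 mm in size". Section 10.5.3 frames the blockade question as one "in patients with extrahepatic metastases".
- **Tracer.** Section 8.3.1 states that 18F-FFNP "is primarily cleared from the body via hepatobiliary elimination".
- **Finding lesions.** Section 10.5.4: "Lesions of interest will be visually identified by 18F-FFNP uptake and confirmed on at least one other conventional imaging modality". It adds: "Each site of disease will be analyzed for (1) qualitative and (2) quantitative 18F-FFNP uptake". On number: "For subjects with innumerable lesions, an arbitrary maximum of five lesions will be recorded".
- **Uptake filter.** Section 10.5.5 grades uptake on five levels against background. Only the top two, moderate and intense, count as increased. Background is not defined.
- **Target lesions.** Section 10.5.6: "Up to five target lesions with increased 18F-FFNP uptake, as defined by the qualitative analysis, will be further evaluated".
- **Classification.** Section 10.5.7 calls a subject *complete* if every target has fallen by more than 75%, or every target has SUVmax below 1.5 on the second scan. The *incomplete* clause opens "If the SUVmax for any of the five lesions has not decreased by > 75" (per cent), and also applies if any new lesion appears with SUVmax of 1.5 or more.

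None of sections 10.5.4 to 10.5.7 limits target or new lesions by organ or by size.

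**The concern.** The entry rule shows that site and size mattered to the authors. It requires only one qualifying lesion, however, so an eligible subject may also have liver lesions or lesions under 10 mm, and nothing keeps these out of the classification.

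The classification turns on the worst lesion: one failing target is enough for *incomplete*, whatever the others show. For a tracer cleared through the liver and bile, some activity in and around a liver lesion may not be receptor binding, and a receptor antagonist would not be expected to remove that part. A liver target could therefore fail the 75% criterion in a subject whose receptors are blocked.

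What is at stake is the reading of the sub-study. Section 10.5.3 interprets incomplete blockade as a sign of suboptimal dosing and suggests that it may go with earlier progression. A false *incomplete* label feeds directly into both interpretations.

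**Working it through.** The plan gives no figure to reproduce here, and no liver or background SUV. The thresholds (75% and 1.5) come from section 10.5.7. All SUVs below are assumptions, shown as ranges. I read the references in section 10.5.7 to five lesions as meaning all targets, since section 10.5.6 allows fewer.

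**1. Liver target.** Let B be its baseline SUVmax and L the liver background. Suppose that at full blockade it falls to L and no further. Then:

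- Fall = 1 − L/B. A fall above 75% requires L/B < 0.25, that is B > 4L.
- For L = 2, 3 and 5, B must exceed 8, 12 and 20.
- For B/L = 2, 3, 4 and 5, the fall is 50%, 67%, 75% and 80%. The criterion is strict, so only the last passes.
- The other route to *complete*, SUVmax below 1.5, is closed on the same supposition once L is 1.5 or more.

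A liver lesion at two or three times local background could be graded moderate, become a target, and then fail at full blockade.

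**2. Effect on the subject.** If each liver target independently has chance q of failing falsely, the chance of a false *incomplete* with m such targets is 1 − (1 − q)^m. For q = 0.1, 0.3 and 0.5 this is 0.10, 0.30 and 0.50 with one target, and 0.19, 0.51 and 0.75 with two. Other targets that pass do not lower it.

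**3. Lesions under 10 mm.** The documents do not say why 10 mm was chosen. As an illustration only, take measured SUV = RC × true SUV + (1 − RC) × background, where RC is the fraction of signal recovered from a small lesion. With a true baseline of 6, a true fall of 80% (to 1.2), RC = 0.5 and background 1.0:

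- Baseline: 0.5 × 6 + 0.5 × 1.0 = 3.50.
- Second scan: 0.5 × 1.2 + 0.5 × 1.0 = 1.10.
- Measured fall: 1 − 1.10/3.50 = 69%, which misses the criterion.

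Over true baselines of 4 to 8 and backgrounds of 0.5 to 1.0, the measured fall is about 72–78% at RC 0.7, 64–75% at RC 0.5 and 51–70% at RC 0.3. The direction is again towards *incomplete*. In all these cases, however, the second-scan value is below 1.5. If every target is below 1.5, the subject meets both definitions at once. That overlap is a separate ambiguity, so the size argument is weaker than the liver one.

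**4. New lesions.** A new lesion anywhere, of any size, with SUVmax of 1.5 or more makes the subject *incomplete*. A limit placed on target lesions alone would leave this route open.

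**The case against.** **The uptake filter may already remove most liver lesions.** If background means adjacent liver, a lesion must stand well above it to be a target. A lesion at 1.5 times liver (largest fall 33% on the supposition above) may be graded mild and dropped. This stands as a limit on frequency. It does not close the gap, because background is undefined and the filter is not a site rule.

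**A reader might infer that a liver lesion can never meet the criterion.** The documents do not support that. The lowest grade in section 10.5.5 is tumor below background, so liver activity is not a proven floor. The formula describes a lesion that falls only to L.

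**A reader might infer that one small lesion can make an unblocked subject *complete*.** It cannot when other targets exist, because *complete* needs every target to pass. It could happen only if such lesions were the sole targets, which is possible since Inclusion 12 does not require uptake in the qualifying lesion.

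**A reader might infer that the choice of the five lesions is declared arbitrary.** In section 10.5.4 that word describes the cap of five. How the five are chosen is not stated.

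**The detail could sit elsewhere.** Section 10.5.3 plans a trial-specific PET manual for coordinators and technologists. Nothing says that it will set lesion selection, and section 10.5.7 presents the definition as prospective.

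**Little depends on it.** Section 6.1.3 makes the scans optional and subject to funding. They are absent from Table 3, have no planned test in section 9, and inform no trial decision. This stands and sets the priority.

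**Conclusion.** The mismatch is real. Entry is defined by an extrahepatic lesion of at least 10 mm, while the blockade label can be decided by a lesion of any site or size. With documented hepatobiliary clearance, following the rule as written can label a blocked subject *incomplete*. This rests on two assumptions: that a liver lesion passes the uptake filter, and that it retains background of at least 25% of its baseline SUVmax. The documents allow neither the frequency nor L to be estimated.

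It would be tempting to go further and put a size on the shift in the complete-blockade rate, or to say that the rule could itself create an association with progression. Neither is supported. Two or three misclassified subjects out of 12 would be 17% or 25%, but that count would be invented. The documents also do not show that liver disease progresses earlier on this treatment. In the phase I study summarised in section 1.4.1.6, two of the three breast cancer patients with stable disease beyond 24 weeks had liver metastases; that is too few to settle the matter either way.

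The response-rate endpoint and the two-stage design are unaffected. This is a cheap improvement to an optional sub-study of up to 12 subjects.

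**What to change.** In sections 10.5.4, 10.5.6 and 10.5.7, state that the target lesions and the new lesions used for the blockade classification must be extrahepatic and at least 10 mm, matching Inclusion 12. Report liver lesions and smaller lesions descriptively. Section 10.5.7 must be included, or the new-lesion clause keeps the same gap.

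I would not add a rule taking the five lesions with the highest baseline SUVmax. Selecting on a high first reading invites regression to the mean, which favours apparent falls and hence *complete*.

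The change costs a few sentences and no extra scan or reading. The downside is that a subject whose qualifying extrahepatic lesion shows no increased uptake may have no target left. The plan should say that such subjects are counted as not evaluable for blockade.

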10.5.7 Definition of 18F-FFNP Blockade

The same five target lesions will be analyzed for quantitative 18F-FFNP uptake on the second 18F-FFNP PET/CT examination as on the initial scan. If the SUVmax for all five lesions have decreased by > 75% or all five lesions have SUVmax < 1.5 on the second scan, then these subjects will be prospectively defined as having complete 18F-FFNP blockade. If the SUVmax for any of the five lesions has not decreased by > 75% or if any new lesions arise with SUVmax ≥ 1.5 , then these subjects will be defined as having incomplete 18F-FFNP blockade. Changes in radiotracer uptake in normal organs with expected 18F-FFNP uptake (pituitary gland and uterus) will also be measured as an internal reference.

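### The two sentences defining complete and incomplete 18F-FFNP blockade in section 10.5.7 do not fit together: a subject can be incomplete although every lesion meets a threshold, or can meet both definitions at once

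*Combined protocol and SAP*

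**What the plan says.** Section 10.5.7 sorts subjects into two classes from the change in lesion SUVmax between the scan before treatment and the scan 7 to 14 days after its start.

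- Complete blockade: "If the SUVmax for all five lesions have decreased by > 75% or all five lesions have SUVmax < 1.5 on the second scan".
- Incomplete blockade, existing lesions: "If the SUVmax for any of the five lesions has not decreased by > 75" per cent.
- Incomplete blockade, new lesions: "or if any new lesions arise with SUVmax ≥ 1.5".

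The classification is declared prospective. Section 10.5.7 speaks of exactly five lesions ("The same five target lesions will be analyzed for quantitative 18F-FFNP uptake on the second 18F-FFNP PET/CT examination as on the initial scan"), whereas section 10.5.6 sets a maximum: "Up to five target lesions with increased 18F-FFNP uptake, as defined by the qualitative analysis, will be further evaluated".

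Section 10.5.3 gives the class its meaning: "Incomplete receptor blockade, indicating suboptimal dosing, may be associated with earlier disease progression". The imaging is optional and "will be performed for up to 12 subjects". Section 9 specifies no analysis of the blockade class.

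**The concern.** The word *or* in the complete sentence joins two conditions, each of which applies to all lesions. One lesion cannot qualify by its relative fall while another qualifies by its low absolute uptake. The incomplete sentence then uses only the relative threshold for existing lesions and leaves out the below-1.5 alternative. The two sentences are therefore not complements of each other.

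What is at stake is the meaning of the label. The protocol reads incomplete blockade as a sign of suboptimal dosing and a possible correlate of earlier progression. If the label also depends on how many lesions a subject has and how varied their baseline uptake is, it is partly a marker of disease extent. That could produce an association with progression without any difference in receptor blockade. With at most 12 subjects, one or two labels that turn on how the text is read can change the result.

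**Working it through.** The plan states no figure for this rule, so there is none to reproduce. The check applies the two sentences as written.

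**When does a lesion meet only one threshold?** Let b be baseline SUVmax and f the second-scan value. The relative threshold is f < 0.25b; the absolute threshold is f < 1.5.

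- Relative only: f < 0.25b and f ≥ 1.5. Then 0.25b > 1.5, so b > 1.5/0.25 = 6.
- Absolute only: f < 1.5 and f ≥ 0.25b. Then 0.25b < 1.5, so b < 6.

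A subject whose lesions are split across the two routes must therefore have at least one baseline above 6 and one below 6, with second-scan values that fit.

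**Worked subjects (illustrative values)**

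| Lesions, baseline → second scan | Falls | Complete sentence met | Incomplete sentence met |
|---|---|---|---|
| 10→2.0; 3.0→1.2 | 80%; 60% | no | yes |
| 8→1.8; 4→1.2 | 77.5%; 70% | no | yes |
| 8→1.6; 4→0.9 | 80%; 77.5% | yes | no |
| 12→2.5; 7→1.6 | 79.2%; 77.1% | yes | no |
| 5→1.4; 3→1.4 | 72%; 53.3% | yes | yes |
| 8→1.4; 4→1.2 | 82.5%; 70% | yes | yes |
| 3.0→1.2 only | 60% | yes | yes |

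In the first two rows every lesion meets a threshold and the subject is still incomplete (fault a). In the last three rows both definitions apply (fault b). If the incomplete sentence governs, the below-1.5 route to complete blockade never takes effect.

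**How often?** The documents give no baseline distribution, spread between lesions or expected fall, so all of these are assumed. The denominator throughout is subjects whose every lesion meets at least one threshold.

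*Assumption set 1:* log-normal baseline, median 3, 5 or 8, log-SD 0.3 or 0.6; residual uptake median 20%, log-SD 0.3; 2, 3 or 5 independent lesions; no background floor. Fault (a): 0.1% to 29%. Fault (b): 1% to 70%.

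*Assumption set 2:* log-normal baseline, median 4 or 6, log-SD 0.5; second-scan value = max(b × (1 − fall), floor) × log-normal noise (SD 0.1); floor 0.8 or 1.0; independent lesions. Fault (a):

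| True fall | 2 lesions | 3 lesions | 5 lesions |
|---|---|---|---|
| 80% | 7–14% | 17–31% | 36–58% |
| 85% | – | – | 13–37% |
| 90% | – | – | 2–11% |

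With five lesions, fault (b) in set 2 is about 8% to 95%.

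Set 2 is sensitive to its assumptions. With five lesions and no floor, fault (a) is about 2% at an 80% fall and 0% at 85% and 90%. With three lesions correlated 0.6 within subject and the floor kept, it is 3–8% at an 80% fall. Fault (b) also vanishes without a floor once the true fall is 85%. Residual uptake is then 0.15b, and missing the relative threshold needs noise above 0.25/0.15 = 1.67, which is ln(1.67)/0.1 ≈ 5.1 SDs.

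**The case against.** The strongest defence is that a strict subject-level rule is a legitimate choice. Sections 10.5.5 and 10.5.6 are headed as lesion-level analyses; section 10.5.7 is not, and it classifies subjects. No document gives a reference standard for blockade or says that lesions may qualify by different routes. This stands as far as it goes: the label in fault (a) cannot be shown to be wrong against an external truth, and the sponsor may have meant the strict reading. It does not answer fault (b), where the text itself gives one subject two labels.

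Several stronger readings are tempting and are not supported:

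- *Any difference in baseline uptake makes a subject incomplete.* It does not. The third and fourth worked subjects have unequal baselines and are unambiguously complete.
- *A subject with only the 3.0 to 1.2 lesion would be plainly complete.* That subject also meets the incomplete sentence, which makes no exception for values below 1.5.
- *The class is the imaging study's main read-out.* Section 10.5.3 says the change in uptake will be evaluated and lists several SUV, ratio and volume measures that do not use the class.
- *More than a third of subjects would be mislabelled.* Figures of that size for fault (a) appear only with five independent lesions and an assumed background floor.
- *A lesion-by-lesion rule would remove the link with disease extent.* Requiring every lesion to be blocked still gets harder as lesions are added. The link is reduced, not removed.

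It is also fair that only lesions with moderate or intense uptake are quantified, which partly excludes the low-uptake lesions that drive both faults. The filter is visual, however, with no SUV cut-off, so nothing keeps lesions below SUVmax 6 out.

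**Conclusion.** The point holds in a limited form. As written, section 10.5.7 (a) can label a subject incomplete although every lesion meets a threshold, when baselines lie on both sides of SUVmax 6 and the second-scan values fit; and (b) assigns both labels to a subject with all lesions below 1.5 but at least one fall of 75% or less.

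Both faults follow from the text and need no assumption. Their frequency does. Among subjects whose every lesion meets a threshold, fault (a) runs from about 0% to 58% and fault (b) from about 0% to 95%, depending on the number of lesions, their baseline uptake, the background floor and the true fall. These ranges are illustrative, not predictions.

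The importance is small: an optional imaging correlative, conditional on funding, in at most 12 subjects. The primary response-rate analysis, PFS and safety do not use the class.

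**What to change.** Rewrite both sentences of section 10.5.7; changing only the complete sentence would leave the contradiction in place. Suggested content:

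- A target lesion is blocked if its SUVmax falls by more than 75% or is below 1.5 at the second scan.
- Blockade is complete if every target lesion (up to five, in line with section 10.5.6) is blocked and no new lesion has SUVmax of 1.5 or more.
- Blockade is incomplete in all other cases.
- Report the proportion of blocked lesions per subject beside the class, because the class still depends on the number of lesions.

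The new-lesion condition belongs in the complete definition because the present complete sentence is silent on new lesions. If the sponsor intends the strict all-lesion reading, it should say so and define incomplete as its exact complement.

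The cost is a short wording change and one extra descriptive summary, with no new data or scans. It should be made before the paired scans are classified, since the definition is meant to be prospective.

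### The SUVmax <1.5 route to complete 18F-FFNP blockade needs no baseline value and no fall, and every subject it alone would admit is also defined as incomplete

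*Combined protocol and SAP*

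**What the plan says.** The rule is in section 10.5.7 of the combined protocol and SAP. Complete blockade is reached by either of two routes:

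- **Relative route:** "If the SUVmax for all five lesions have decreased by > 75"%.
- **Absolute route:** "all five lesions have SUVmax < 1.5 on the second scan".

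The following sentence defines incomplete blockade: "If the SUVmax for any of the five lesions has not decreased by > 75"%, "or if any new lesions arise with SUVmax" of 1.5 or more. It makes no exception for a target lesion that is below 1.5 on the second scan.

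Entry of target lesions is set in sections 10.5.5 and 10.5.6. The quantitative step takes "Up to five target lesions with increased 18F-FFNP uptake, as defined by the qualitative analysis, will be further evaluated". The grading is visual and relative to background: "Tumor uptake will be defined as increased (moderate or intense uptake) or absent (no uptake, minimal or mild uptake"). No SUV number is attached to any grade. The eligibility criterion for the optional PET/CT (inclusion criterion 12) asks for PgR-positive disease and an extrahepatic lesion of at least 10 mm, again without an SUV threshold.

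Section 10.5.3 gives the intended reading: "Incomplete receptor blockade, indicating suboptimal dosing, may be associated with earlier disease progression". Imaging is planned for up to 12 subjects.

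**The concern.** The entry gate is relative to background and the absolute route is a fixed SUV level. Nothing in the plan links the two. The value 1.5 is applied to new lesions on the second scan but not to target lesions at baseline, so a lesion that starts near or below 1.5 can satisfy the absolute route with little or no change.

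Low baselines are foreseeable. PgR positivity needs only 1% of cells (inclusion criterion 4), and section 8.3.1 says that uptake tracks PgR expression.

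The label is meant to show whether onapristone occupies the receptor and whether failure to do so goes with earlier progression. If it partly reflects where a subject started, it mixes baseline PgR level into that comparison. PgR status and expression are themselves examined as predictors of outcome in sections 9.2 and 10.5.1. With at most 12 subjects, one or two labels matter.

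**Working it through.** The plan states no error rate or expected proportion for blockade, so there is no figure to reproduce.

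**Step 1: fall implied by the absolute route.** The inputs are the two thresholds in section 10.5.7. For baseline SUVmax S, the fall needed to reach 1.5 is max(0, 1 − 1.5/S). The two routes coincide where 1.5 = (1 − 0.75) × S, that is S = 1.5/0.25 = 6.0.

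| Baseline SUVmax (illustrative) | Fall needed to reach 1.5 | Second-scan SUVmax must be below, for a fall >75% |
|---|---|---|
| 1.4 | 0% (a rise to 1.45 also passes) | 0.35 |
| 1.6 | 6% | 0.40 |
| 2.0 | 25% | 0.50 |
| 3.0 | 50% | 0.75 |
| 4.0 | 62.5% | 1.00 |
| 6.0 | 75% | 1.50 |

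The absolute route is the looser one only below a baseline of 6.0.

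**Step 2: the two sentences side by side.** Suppose a subject is complete by the absolute route but not by the relative one. Then at least one lesion has not fallen by more than 75%, which is the condition for incomplete. Every such subject therefore carries both labels. Examples, with all lesions equal:

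| Baseline → second scan | Fall | Complete? | Incomplete? |
|---|---|---|---|
| 1.4 → 1.4 | 0% | yes | yes |
| 2.0 → 1.4 | 30% | yes | yes |
| 5.0 → 1.4 | 72% | yes | yes |
| 8.0 → 1.4 | 82.5% | yes | no |
| 8.0 → 2.1 | 74% | no | yes |

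If incomplete takes precedence, the absolute route never changes a classification. If complete takes precedence, the missing floor and missing minimum fall take full effect.

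**Step 3: possible frequency if complete governs.** The documents give no baseline or background SUV, no repeatability figure and no lesion counts. All of the following are assumptions: lognormal true SUVmax with median 2.0 to 4.0; between-lesion CV 30% to 50%, with half the log-variance shared within a subject; independent scan error with CV 15%; no drug effect; no visual gate; 200,000 simulated subjects per scenario. The table gives the percentage of subjects with all lesions below 1.5 on the second scan.

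| Median baseline | 1 lesion | 2 lesions | 3 lesions | 5 lesions |
|---|---|---|---|---|
| 2.0 | 19–28% | 7–14% | 3.5–8% | 1.3–4% |
| 2.5 | 6–15% | 1–6% | 0.5–3% | 0.1–1.1% |
| 3.0 | 2–8% | 0–2% | under 1% | 0.3% or less |
| 4.0 | 0–2% | under 1% | about 0% | about 0% |

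In the same runs the relative route gave essentially 0%, and every subject counted as complete also met the incomplete rule.

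**Step 4: effect of a floor.** With one lesion at median 2.0, a baseline floor of 1.5 lowers the no-effect rate from 19–28% to 8–9% of evaluable subjects. A true 30% fall would still be called complete in about 39–49% of them, so a floor alone does not make the absolute route a measure of change. Adding a 40% minimum fall, purely as an illustration, brings the no-effect rate below 1%.

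**The case against.** Four objections carry weight.

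**The plan does not simply call these subjects blocked.** A reader might infer that the complete-blockade proportion is biased upward. The documents do not support that as an unconditional claim. The incomplete sentence covers every subject in question, and if it governs, the bias is zero. This stands. It does not clear the rule, because the absolute route is then redundant, and settling precedence in favour of complete without further change would fix the weakness in place.

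**There is a baseline gate.** A reader might infer that any faint lesion can be a target. It cannot: lesions with no, minimal or mild uptake are excluded. This narrows the problem to lesions that look well above background yet have a low SUVmax. Because the gate is visual and background SUV is not given, such lesions are neither ruled out nor shown to be common. The simulation omits the gate. At median 2.0 with one lesion, 64–80% of its positives come from lesions with a measured baseline below 1.5, which the gate may already remove.

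**The high rates belong to the least favourable case.** The rule is worded for five lesions, where the rate is 4% or less. Section 10.5.6 allows fewer, but the mix is unknown.

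**The stakes are small.** The scans are optional and depend on funding (section 6.1.3). Blockade is not an endpoint in Table 3, and section 9 specifies no test of it. Section 10.5.3 also plans to evaluate the change in several uptake measures, so the binary label is not the only readout. All of this stands and sets the grade.

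**Conclusion.** The point holds as a defect of definition. The absolute route has no numeric baseline requirement and no minimum fall, so below a baseline SUVmax of 6.0 it accepts falls of 75% or less, and at or below 1.5 no fall at all. That follows from the plan's own thresholds. The adjoining sentence gives the same subjects the opposite label, and no precedence is stated.

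The frequency is not established. The range of about 0% to 28% with one lesion and 0% to 4% with five rests on assumed baselines, assumed variability, complete taking precedence and no visual gate. It would be tempting to read the upper end as a forecast that about 0.28 × 12 = 3.4 of 12 subjects would be mislabelled. The documents do not support that: it would need every subject to have a single lesion drawn from a distribution centred on 2.0. If baselines lie mostly above 4, the effect is small.

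This is a minor finding, confined to an optional exploratory substudy. ORR is unaffected.

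**What to change.** Amend sections 10.5.6 and 10.5.7 together, before any images are read:

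1. Count a target lesion toward blockade only if its baseline SUVmax is at least 1.5, the level already used for new lesions.
2. Report subjects with no such lesion separately, as not evaluable for blockade.
3. State which definition governs when all target lesions are below 1.5 on the second scan but at least one has fallen by 75% or less.
4. Apply the rule to all target lesions present, from one to five.
5. If the <1.5 route remains sufficient for complete blockade, also require a prespecified minimum fall larger than scan repeatability. The imaging team should set the value; the 40% used above is only an illustration and is open to debate.

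The cost is a few sentences and no extra scans. The downside is that a few of the up to 12 subjects may become not evaluable, and the reported complete-blockade proportion may be lower.
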